### 1.1.3 Determination of Sample Size

Approximately 10 subjects will be enrolled sequentially at progressively shorter infusion durations, beginning with the 60-minute infusion duration, progressing down to the 45-minute infusion duration and then to the 30-minute infusion duration. Approximately 110 subjects are planned to be enrolled into a desirable infusion cohort that does not meet the dose limiting criteria. Therefore, the total number of subjects enrolling across the 3 different cohorts in the study is approximately 130.

Based on the MIRROR-RCT study, we expect approximately 5.0% of subjects to have an IR (including events of anaphylaxis) when taking pegloticase concurrently with MTX. The sample size of 110 for the selected cohort is chosen to ensure a high probability of ruling out an unacceptably high IR rate. If the observed IR rate is 5%, there is a greater than 80% probability that the upper bound of the two-sided 95% exact confidence interval for the IR rate is less than 13%.

[figure not shown]
## 1.2 Efficacy Assessments

### 1.2.1 Serum Uric Acid

Serum samples for measurement of sUA levels will be collected at the Screening Visit, Week -4 and Week -2 Visits during the MTX Run-in Period; within 48 hours prior to each pegloticase infusion and after the end of each pegloticase infusion prior to discharge, from Day 1 in the Pegloticase + MTX Period through Week 22; and at the End of Pegloticase Infusion Visit (if applicable); at the Week 24/End of study/Early Termination Visit and Month 3 Post-Treatment Follow-Up visits.

A subject with pre-infusion sUA level > 6 mg/dL (based on the local or central laboratory) at 2 consecutive study visits, beginning with the Week 2 Visit, will be discontinued from pegloticase treatment and remain on study.

Samples that result in discordant results between local and central laboratories will be evaluated and discussed with the Investigator and the Sponsor's Medical Monitor on a case-by-case basis to determine whether the subject should continue on study or discontinue.

### **1.3 Safety Assessments**

Safety will be assessed via AE and concomitant medication (CM) use monitoring, physical examinations, vital signs, clinical safety laboratory evaluations (hematology, chemistry, urine albumin: creatinine ratio), pregnancy testing (if applicable), ECGs and AESIs (i.e., IRs, anaphylaxis, gout flares and cardiovascular events).

All adverse events will be coded using Medical Dictionary for Regulatory Activities (MedDRA Version 23.0). Medications will be coded using World Health Organization Drug Dictionary (WHO-DD Global B3 March 2020).

AESIs defined in the protocol for adjudication (See protocol Section 9.6.1.2.1.5) are IRs, anaphylaxis and cardiovascular events. These will be adjudicated by an external committee of subject matter experts. The AESI of gout flare will not be adjudicated.

### **1.4 Pharmacokinetic and Anti-drug Antibody Measurements**

#### **1.4.1 Pegloticase Pharmacokinetics**

For all subjects, serum samples for pegloticase PK analysis will be collected approximately 15 minutes to 2 hours after the end of infusion on Day 1; prior to infusion and approximately 15 minutes to 2 hours after the end of the infusion at Weeks 2, 6, 12 and 20. An additional PK sample will be collected at the End-of-Study (Week 24)/Early Termination Visit.

#### 1.4.2 Anti-drug Antibody (ADA) Measurements

Immunogenicity of pegloticase will be assessed in serum samples by evaluating anti-PEG and anti-uricase immunoglobulin G (IgG) antibodies. Samples will be collected prior to the pegloticase infusion on Day 1 and at the Weeks 2, 6, 12, 20 and the End-of-study (Week 24)/Early Termination Visit and 3-month Post-Treatment Follow-up Visits. In the event of an AE suspected to be an IR, a serum sample will be collected at that time or at the subsequent visit for evaluation of pegloticase antibodies.

#### 1.4.3 MTX Polyglutamate Measurements

Blood samples for MTX polyglutamate measurements will be collected prior to pegloticase infusion on Day 1, Weeks 14, 22, End of Pegloticase Infusions Visit (if applicable) and Week 24 Visits during the Pegloticase + MTX Period.

### 1.5 Endpoints

#### 1.5.1 Primary Endpoint

[figure not shown]
The primary endpoint is the incidence of subjects experiencing IRs (including anaphylaxis) related to pegloticase from Day 1 to Week 24 in the cohort chosen to be the most desirable duration for infusion.

[figure not shown]
#### 1.5.2 Secondary Endpoints

The secondary endpoints will be assessed for the cohort chosen to be the most desirable duration for infusion and include:

- The proportion of Month 6 (Weeks 20, 22 and 24) responders, defined as subjects achieving and maintaining sUA < 6 mg/mL for at least 80% of the time during Month 6.
- The proportion of subjects who experienced any of the following events: IR leading to discontinuation of treatment, anaphylaxis, or meeting Individual Subject sUA Discontinuation Criteria.
- Time to any of the following events: IR leading to discontinuation of treatment, anaphylaxis, or meeting Individual Subject sUA Discontinuation Criteria (two consecutive pre-infusion sUAs > 6 mg/dL).

#### 1.5.3 Exploratory Endpoints

#### 1.5.4 Safety Endpoints

- Incidence of IRs, anaphylaxis, gout flares, cardiovascular events and the AE/SAE profile overall and potentially attributed to the combination of pegloticase and MTX.
- The proportion of subjects who experienced IR leading to slowing down of the infusion rate or discontinuation of treatment.
- The time to first IR leading to slowing down of the infusion rate or discontinuation of treatment.
- Time to first IR.
- The proportion of subjects who were able to complete all infusions over the assigned treatment duration length or a lesser time, without clinically requiring an increased infusion time.
- The proportion of infusions completed over the assigned duration length or a lesser time, without clinically requiring an increased infusion time.
- Laboratory tests: change from baseline to each scheduled assessment.
- Vital signs: change from baseline to each scheduled assessment.

#### 1.5.5 Pharmacokinetic and Anti-drug Antibody Endpoints

- PK of pegloticase.
- Incidence and titer of anti-PEG and anti-uricase IgG antibodies.

### 1.6 Treatment Periods

- MTX Run-in Period
  - For summaries by study visit, only includes Week -4 and Week -2 study visits

- For assignment of study period to ongoing assessments (e.g. AE or CM), includes all activities from the date and time of first MTX dose to the date and time of the first dose of pegloticase.
- Pegloticase + MTX Period
  - For summaries by study visit, includes all visits starting with Day 1 through Week 24 and/or End of Pegloticase visit
  - For assignment of study period to ongoing assessments (e.g. AE or CM), includes all activities from the date and time of the first dose of pegloticase to the date of the Week 24 and/or End of Pegloticase visit

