### 9.6.1.10 Assessment of Gout Flare

There is no validated instrument to assess gout flares. Gout flares will be assessed at the time points specified in [Section 2.1](#). Investigators will assess gout flares based on subject questioning and/or direct observation. All gout flares will be recorded as adverse events with the required AE reporting information.

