Unknown	Unknown	Yes	Yes	Yes	Yes
Unknown	< first dose of MTX	Yes	No	No	No
Unknown	≥ first dose of MTX and < first dose of Pegloticase	Yes	Yes	No	No
Unknown	≥ first dose of Pegloticase and ≤ 30 days after last	Yes	Yes	Yes	No

Medication Start Date	Medication End Date	Prior	Concomitant in MTX Run-in Period	Concomitant in Pegloticase + MTX Period	Follow-up (> 30 days after last dose of Pegloticase or MTX in the Pegloticase + MTX Period)
	Pegloticase/MTX dose				
Unknown	≥ first dose of Pegloticase and > 30 days after last Pegloticase/MTX dose	Yes	Yes	Yes	Yes
< first dose of MTX	Unknown	Yes	Yes	Yes	Yes
≥ first dose of MTX and < first dose of pegloticase	Unknown	No	Yes	Yes	Yes
≥ first dose of pegloticase and ≤ 30 days after last pegloticase/MTX dose	Unknown	No	No	Yes	Yes
> 30 days after last pegloticase/MTX dose	Unknown	No	No	No	Yes

Any medication with a start date prior to the date of first dose of treatment in the MTX Run-in Period will be considered a prior medication.

The following medications will be considered concomitant in the MTX Run-in Period:

- A medication with a start date on or after the first dose date of MTX in the MTX Run-in Period but excluding medications with:
  - Start date on or after the first infusion date of pegloticase and
  - Start date more than 30 days after the last MTX dose, for subjects who did not receive an infusion of pegloticase.
- Medications with a partial start date with month and year of start provided and the year of start and month of start match the month and year of first MTX date and match the month and year of first pegloticase infusion will be classified as being used in the MTX Run-in Period and in the Pegloticase + MTX Period.
- A medication with a start date prior to the first dose date of MTX in the MTX Run-in Period with a stop date strictly after the first dose date of MTX in the MTX Run-in Period

- A medication with a start date prior to the first dose date of MTX in the MTX Run-in Period that was ongoing.

The following medications will be considered concomitant in the Pegloticase + MTX Period:

- A medication with a start date on or after the first infusion date of pegloticase but excluding medications with start date more than 30 days after the date of the end of the last pegloticase or MTX infusion.

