### 3.6.3 Adverse Events

#### 3.6.3.1 Definitions by Period

AEs will be classified as pre-treatment, treatment-emergent AEs (TEAEs) during the MTX Run-In Period, TEAEs during the Pegloticase + MTX period, or Follow-up AEs. The AE's will be classified as follows:

- Pre-treatment: Onset date prior to the first dose of MTX.
- TEAE during the MTX Run-in Period: Onset date on or after the first dose of MTX until the first pegloticase infusion.
- For subjects who do not receive pegloticase, also include AEs with onset date within 30 days after the last dose of MTX.
- TEAE during the Pegloticase + MTX Period: Onset date on or after the start of the first pegloticase infusion through 30 days after the last dose of pegloticase and/or MTX (whichever is later).
- Follow-up AE: Onset date >30 days after last dose of pegloticase and/or MTX (whichever is later).

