#### 3.6.3.2 Overall Summaries

An overall summary of TEAEs for the ITT analysis set will be provided for the MTX Run-in Period, including the number and percentage of subjects with each AE type as well as the number of events for each of the following:

- TEAEs
- Serious TEAEs
- TEAEs related to MTX
- Serious TEAEs related to MTX
- TEAEs with a Rheumatology Common Toxicity Criteria (CTC) of 3 or higher
- TEAEs leading to permanent withdrawal of MTX
- TEAEs related to MTX leading to permanent withdrawal of MTX
- TEAEs leading to death

An overall summary of TEAEs for the safety analysis set will be provided for the Pegloticase + MTX Period, including the number and percentage of subjects with each AE type as well as the number of events for each of the following:

- TEAEs

- Serious TEAEs
- TEAEs related to pegloticase
- TEAEs related to MTX
- Serious TEAEs related to pegloticase
- Serious TEAEs related to MTX
- TEAEs with a Rheumatology CTC of 3 or higher
- TEAEs leading to permanent withdrawal of pegloticase
- TEAEs related to pegloticase leading to permanent withdrawal of pegloticase
- TEAEs leading to permanent withdrawal of MTX
- TEAEs related to methotrexate leading to permanent withdrawal of MTX
- TEAEs leading to death
- TEAEs of special interest

An overall summary of Follow-up AEs for the safety analysis set will be provided, including the number and percentage of subjects with each AE type as well as the number of events for each of the following.

- AEs
- Serious AEs
- AEs with a Rheumatology CTC of 3 or higher
- AEs leading to death

Percentages for the overall summary of AEs during follow-up will be based on the number of subjects in the safety analysis set who had follow-up more than 30 days after last dose of medication.

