  - Standardized MedDRA Queries (SMQ): Myocardial infarction (broad), Ischaemic Central Nervous System (CNS) Vascular conditions (narrow); Haemorrhagic central nervous system vascular conditions (narrow), Central nervous system vascular disorders, not specified as haemorrhagic or ischaemic (narrow), Embolic and thrombotic events (arterial, venous, vessel type unspecified and mixed arterial and venous) (narrow), Cardiac failure (broad), shock-associated conditions (narrow), Torsade de pointes/QT prolongation (narrow), Arrhythmia related investigations, signs and symptoms (broad), Cardiomyopathy (broad), Supraventricular tachyarrhythmias (narrow), Ventricular tachyarrhythmias (narrow), Conduction defects (narrow)
  - All PTs under SOC of Cardiac disorders
  - HLT Aneurysm
- For non-fatal myocardial infarction: SMQ Myocardial infarction (broad)
- For non-fatal stroke: SMQ: Ischaemic Central Nervous System (CNS) Vascular conditions (narrow); Haemorrhagic central nervous system vascular conditions (narrow); Central nervous system vascular disorders, not specified as haemorrhagic or ischaemic (narrow)
- Congestive heart failure: SMQ Cardiac failure (broad)

The cardiovascular events identified using the aforementioned criteria and the adjudicated cardiovascular events will be summarized by SOC and PT for the MTX Run-in Period and Pegloticase + MTX Period for the safety analysis set. EAIR of pegloticase and MTX will be summarized for the Pegloticase + MTX Period.

The number and percentage of subjects who experienced a gout flare (recorded in the AE eCRF), and number of gout flares per subject will be summarized for the MTX Run-in Period using the ITT analysis set. Percentages will be based on the number of subjects in the ITT analysis set.

The number and percentage of subjects who experienced a gout flare and number of gout flares per subject during the MTX Run-in Period and the Pegloticase + MTX Period (recorded in the AE eCRF) will be provided for the safety analysis set.

Data for the MTX Run-in Period and Pegloticase + MTX Period will be summarized separately, where applicable.

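### SAP 1.6 and SAP 3.6.3.1 end the Pegloticase + MTX Period on different dates, so gout-flare and cardiovascular counts can disagree with the TEAE tables

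*SAP*

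**What the plan says.** SAP 1.6 states its own scope: "For assignment of study period to ongoing assessments (e.g. AE or CM"). For these records the Pegloticase + MTX Period runs from the "first dose of pegloticase to the date of the Week 24 and/or End of Pegloticase visit".

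SAP 3.6.3.1 defines a TEAE of the same named period as one with onset from the start of the first infusion "through 30 days after the last dose of pegloticase and/or MTX (whichever is later"). Anything later is a Follow-up AE. Protocol 9.7.7 has the same 30-day rule.

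SAP 3.3.6 decides which medications are concomitant in the period by their start date, "excluding medications with start date more than 30 days after the date of the end of the last pegloticase or MTX infusion".

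SAP 3.6.3.4 asks for the number and percentage of subjects with a flare, and the number of flares per subject, during the run-in "and the Pegloticase + MTX Period (recorded in the AE eCRF) will be provided for the safety analysis set". Cardiovascular events are summarised for the same two periods, with an exposure-adjusted rate (EAIR) for the second. Neither instruction uses the term TEAE or gives an end date.

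Gout flares also feed the TEAE tables. Protocol 9.6.1.10 says: "All gout flares will be recorded as adverse events with the required AE reporting information". The overall summary in SAP 3.6.3.2 has a row for "TEAEs of special interest", and flares are one of the special-interest categories.

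**The concern.** One period name has two end rules, and 1.6 explicitly claims adverse events. A programmer who takes the flare table's period from 1.6 and the SOC/PT tables from 3.6.3.1 would count the same flare in one output and not in the other.

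The *and/or* in 1.6 adds a second ambiguity. A subject who stops pegloticase early and remains on study attends an End of Pegloticase visit, within about two weeks of the last infusion, and later a Week 24 visit (Protocol 2.1 footnote 3 and 9.4.3.1.1). The SAP does not say which one closes the period.

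The direction matters. If Week 24 closes it, an early stopper can contribute months of off-drug events to a pegloticase + MTX summary, although SAP 3.4 adopts a while-on-treatment strategy for safety endpoints. Protocol 9.5.10 allows oral urate-lowering therapy to restart after the End of Pegloticase laboratory samples, and Protocol 9.5.7.3.2.3 notes that flares often increase when such therapy begins. If the End of Pegloticase visit closes it, some treatment-emergent events fall outside the flare and cardiovascular summaries.

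**Working it through.** The plan gives no figure to reproduce here. The check sets the windows side by side on the SAP's visit calendar.

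**Inputs**
- Target day = 7 × week + 1. This reproduces SAP 3.1.5 Table 1: Week 6 = 43, Week 8 = 57, Week 22 = 155, Week 24 = 169.
- Last MTX dose in completers: Week 23 (Protocol 2.1), so 7 × 23 + 1 = Day 162.
- End of Pegloticase visit: up to 14 days after the last infusion (Protocol 2.1 footnote 3).
- MTX stops when pegloticase stops early (Protocol 9.4.3.1.1). The exact last dose date is an assumption, taken over a range below.

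**Completer.** TEAE window: 162 + 30 = Day 192. Period under 1.6: Day 169. Difference: 192 − 169 = 23 days (Days 170 to 192), or 23/192 = 12% of the TEAE window. A flare in those days is a TEAE under 3.6.3.1. It lies outside the 1.6 period and is too early to be a Follow-up AE.

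**Subject last infused at Week 6 (Day 43), infusion withheld at Week 8 (Day 57).** The End of Pegloticase visit is at the latest on 43 + 14 = Day 57. There are two assumptions for MTX:
- last dose no later than the last infusion: TEAE window ends 43 + 30 = Day 73;
- last dose about Day 55, taken 1 to 3 days before the planned Week 8 infusion (Protocol 9.1): TEAE window ends 55 + 30 = Day 85.

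| Reading of 1.6 | 1.6 end | Against TEAE end Day 73 | Against TEAE end Day 85 |
|---|---|---|---|
| End of Pegloticase visit | Day 57 | 73 − 57 = 16 days shorter | 85 − 57 = 28 days shorter |
| Week 24 visit | Day 169 | 169 − 73 = 96 days longer | 169 − 85 = 84 days longer |

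An End of Pegloticase visit before Day 57 would widen the first row.

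**Other stopping times, Week 24 reading, last MTX no later than the last infusion.** The excess over the TEAE window is 169 − (last infusion day + 30):
- Week 2 (Day 15): 124 days
- Week 12 (Day 85): 54 days
- Week 18 (Day 127): 12 days
- Week 20 (Day 141): −2 days, so the TEAE window then ends later.

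All days are targets; visits may move by ±3 days.

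**Cardiovascular EAIR.** Under SAP 3.6.3.3, person-time for a subject without the event ends at the last dose. A longer event window therefore adds events without adding person-time for event-free subjects.

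**The case against.** The best defence is that the specific rule beats the general one. SAP 3.6.3.1 opens the adverse event section and defines AE classes by period, and 3.6.3.4 is a subsection of that same section. The table in 3.6.3.3 uses the period names as column heads for TEAE rows, and 3.6.3.2 treats special-interest events as TEAEs. The laboratory, vital-sign and ECG rules (SAP 3.6.4 and 3.6.5) also use 30 days. On that reading 1.6 is a leftover sentence, and every AE table uses one window.

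This may well be how the tables are programmed, so the point can only be that the counts *can* differ. The text does not require the benign reading, however. Section 1.6 names AEs as within its scope, and 3.6.3.4 uses the period name without calling the events treatment-emergent. Protocol 9.7.7 does not settle it, because SAP 3.1 says the SAP supersedes the protocol's statistical sections.

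Three further objections stand:
- A reader might infer that events are lost. They are not. AEs are collected through the 3-month follow-up visit, and a flare dropped from the flare summary under 1.6 stays in the TEAE tables and the listings.
- Medications have their own explicit rule in 3.3.6, and no second medication table relies on 1.6. The conflict there is one of wording and produces no competing count.
- The affected outputs are descriptive, and the SAP plans no inferential testing.

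**Conclusion.** The inconsistency is real: the same named period has two end rules for AEs, and one of them is ambiguous for early stoppers. Its effect depends on 3.6.3.4 being programmed from 1.6. In that case the windows differ by 23 days for completers. For a subject last infused at Week 6 the 1.6 period is about 16 to 28 days too short or 84 to 96 days too long. The completer figure rests on scheduled dosing; the early-stopper ranges rest on the assumed last MTX date.

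The exposed outputs are gout-flare and cardiovascular counts, the cardiovascular EAIR, and the period of onset shown in the AE listings.

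Two stronger readings are not supported. The first is that the trial's main results are at risk. The primary endpoint (SAP 3.4.1) covers Day 1 to Week 24 and counts only events while the subject is receiving pegloticase. The event-based secondary endpoints (3.4.2.2) have the same on-treatment restriction, and the Month 6 response (3.4.2.1) rests on sUA. The second is that a definite number of subjects or events will be miscounted. The documents do not state how many subjects are expected to stop early on MTX, or how often flares or cardiovascular events fall in the disputed days.

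**What to change.** In SAP 1.6, end the Pegloticase + MTX Period for AEs and medications 30 days after the later of the last pegloticase and last MTX dose, as in 3.6.3.1, and remove the *and/or* visit wording from that bullet. In 3.6.3.4, state that the gout-flare and cardiovascular summaries use this window and that later events belong to the Follow-up Period. A completer's period would then end on Day 192 in every AE output, and an early stopper would have one end date.

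The cost is one sentence in 1.6 and one cross-reference in 3.6.3.4. Under SAP 3.1 this goes into an SAP amendment if made before database lock. No new data are needed, since AEs are already collected through the 3-month follow-up, and no clinical rule changes.

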## 2 Analysis Sets

The statistical analyses will be performed based on the following analysis sets:

- Intent-to-treat (ITT) analysis set: all subjects who take at least one dose of MTX.
- Modified intention-to-treat (mITT) analysis set: all subjects who receive at least 1 dose of pegloticase. All efficacy analyses will be conducted on the mITT analysis set.
- Safety analysis set: all subjects who receive at least 1 dose of pegloticase. All safety analyses will be conducted on the safety analysis set.
- Pharmacokinetic (PK) set: all subjects who receive at least 1 dose of pegloticase and have a post-pegloticase sample evaluable for PK analysis.

## 3 Statistical Methods

### 3.1 General Methods

Any changes to the finalized SAP made prior to database lock will be documented in an SAP amendment. Any changes to the planned analyses after database lock will be documented in the clinical study report (CSR).

Some of the analyses detailed here may be more explicit or in some aspects different from those stated in the protocol. In case of differences, this SAP supersedes the statistical sections in the protocol.

#### 3.1.1 Reporting Conventions

The formats for the tables, listings, and figures described in this SAP will be provided in a companion document. Changes to the formats of these reports that are decided after the finalization of the SAP will not require an amendment. In addition, any additional supportive or exploratory analyses requested after SAP approval will not require amendment of the SAP. These additional analyses will be described in the CSR.

Study data from the electronic case report forms as well as relevant derived variables will be provided in subject data listings. An indication of specific listings for each data type may be indicated in the text of subsequent SAP sections. Data listings supplied as part of the CSR will be sorted by study center number concatenated with subject number, assessment dates, and time point, if collected.

The following conventions will be applied to all data presentations and analyses:

Continuous variables will generally be summarized by the number of subjects, mean, standard deviation, median, minimum, and maximum. Unless otherwise specified, the minimum and maximum values will be displayed to the same number of decimal places as the raw data, the mean and median will be presented to one extra decimal place compared to the raw data, and the standard deviation will be displayed to two extra decimal places compared to the raw data

Categorical variables will be summarized using frequencies and percentages within each category. Unless otherwise specified, the percentage will be presented in parentheses to one decimal place. Frequency and percentage values of 0 will be presented as '0' rather than '0 (0)'.

Unless otherwise specified, time to event data will be reporting using weeks as the timescale.

All summary tables will include the analysis set sample size (i.e., number of subjects).

Date variables will be formatted as DDMMYY for presentation.

Unless otherwise specified, confidence intervals (CI) will be based on two-sided 95% confidence.

If multiple assessments occur at a given post-baseline time point, the latest value will be used.

There will be no statistical testing to make an inference.

